5.1.3 Removal of Subjects from the Study

Subjects will be informed that they are free to withdraw from the study at any time. Subjects should be questioned for the reason of premature withdrawal, although they are not obliged to disclose it. This needs to be fully documented in the Source Document and electronic Case Report Form (eCRF).

When a subject withdraws or is removed from the study, the whole examination procedure planned on Day 6 must be performed as soon as possible after the time of withdrawal unless the subject has withdrawn their informed consent to do so. After the time of withdrawal, the subject will enter into the 7-day period of safety follow-up. Subjects withdrawn or removed from the study cannot re-enter the study.

Subjects must be withdrawn from the study for any of the following reasons:

- Withdrawal of informed consent.
- Any AE or condition (including clinically relevant changes in a laboratory parameter), at the discretion of the Investigator.
- Positive pregnancy testing (any invasive procedures, including the drawing of blood MUST NOT be performed after diagnosis of pregnancy, see Section 8.5).
- The Sponsor or Principal Investigator terminates the study. If the Sponsor or the Principal Investigator decide to prematurely terminate the study, the head of the medical institution should be reported the fact and the reason in writing promptly.
- Withdrawal is considered to be in the best interest of the subject or the other subjects.
- The subject wish to quit smoking (this is applicable for all subjects during screening to the baseline period and for subjects allocated to THS 2.2 or CC arms during the exposure period).

Subjects may be discontinued from the study for any of the following reasons:

- Lost to follow-up.

- Concomitant treatment with non-authorized medication as defined in the context of this study (in general, any concomitant medication should be discussed with the CRO Medical Monitor on an ongoing basis).
- If a subject uses any CC or nicotine/tobacco-containing product other than the product/regimen he/she is assigned to, it will be at the discretion of the Investigator to decide whether or not to withdraw the subject from the study.
- Non-compliance to the study procedures.

Subjects withdrawn prematurely after randomization will not be replaced and will not be allowed to re-enter the study. All subject withdrawals have to be documented properly in the source documentation and the eCRF.

5.1.4 Violation of Selection Criteria

Subjects who are eligible at Screening, but who do not meet the entry criteria at Admission Day (Day -2) will be considered a screening failure and will be replaced by other subjects.

Subjects who violate the entry criteria prior to enrolment, but who were considered eligible, will be immediately withdrawn from the study when the violation is detected. If subjects are not yet randomized, they can be replaced.

6 INVESTIGATIONAL PRODUCTS

6.1 Description of Investigational Products

6.1.1 Test Product

THS 2.2 comprises the following components: Tobacco Stick, Holder, Charger, a Cleaning Tool, a mains power supply, and a USB cable:

Confidentiality statement: Data and information contained in this document are considered to constitute trade secrets and confidential commercial information, and the legal protections provided to such trade secrets and confidential information are hereby claimed under the provisions of applicable law. No part of this document may be publicly disclosed without the written consent of Philip Morris Products S.A.

Charger:	The function of the Charger (Model 4) is to recharge the Holder after use. It contains a battery with sufficient capacity to recharge the Holder approximately 20 times. It is a convenient size to carry around, and can itself be recharged from a mains power source.
Tobacco Stick Holder (Holder):	The function of the Holder (Model 4.2) is to heat the Tobacco Stick, delivering an aerosol to the user. The electrical heating is powered from an internal battery which delivers power for about 6 minutes (allowing complete use of a single Tobacco Stick).
THS Tobacco Stick (Tobacco Stick):	The Tobacco Stick (product code C3) contains tobacco which, when heated, generates an aerosol. It is custom-designed to be used with the Holder.

The overall objective of the product design is to provide an acceptable experience in which the HPHCs levels in the aerosol are substantially reduced in comparison with CC.

The THS 2.2 will be provided by the Sponsor.

Per cigarette/Tobacco Stick tar, nicotine, and carbon monoxide yields are normally determined by standardized test methods. The most widely used test method is ISO 4387. PMI has developed a modified version of this method, which improves the determination of tar in products with high water content, which is typical for heated tobacco products (PMI, 2012, PMI, 2013a, PMI, 2013c). Another method is the more intensive smoking method developed by Health Canada (Health Canada, 1999).

Table 1 below lists the commonly reported measures (PMI, 2013).

Table 1. Measured Aerosol Fractions for the THS Tobacco Sticks

Constituent (mg/THS Tobacco Stick)	ISO ¹	Health Canada Intense regime ²
Tar(NFDPM)	4	10.3
Nicotine	0.5	1.32
Carbon monoxide	1	0.6

¹ International Organization for Standardization ISO machine-smoking regimen. The analytical method has been modified to avoid inaccuracies as a result of condensation from high water-content aerosols.

² Health Canada Intense machine-smoking regimen (55 mL puff volume, 2-second puff duration, 30-second

Constituent (mg/THS Tobacco Stick)	ISO ¹	Health Canada Intense regime ²
inter-puff interval) (Health Canada, 1999)		
³ NFDPM: Nicotine-free dry particulate matter		

6.1.2 Reference Product / Baseline Period Products

During the run-in period (Admission to clinic until 06:29 AM of Day -1) and the baseline period (from 06:30 AM of Day -1 until 06:29 AM of Day 1), all subjects will continue smoking their preferred commercially available single brand of non-menthol CC. Subjects are not allowed to roll their own CC.

The reference product to the THS 2.2 during the randomized exposure period is the subject's own preferred commercially available single brand of non-menthol CC.

All eligible subjects will be asked to purchase their own preferred single brand CC prior to Admission and provide his/her anticipated amount of CC for a total of 9 days plus 4 extra packs on Day -2 (Admission Day) to the site study collaborator. The CCs will not be provided by the Sponsor.

6.1.3 Packaging and Labeling

At Admission, all study subjects will provide the anticipated amount of CC in sealed packs to the study site collaborator. The CC packs provided by the subjects should not be opened and the cellophane wrapper should be intact.

Each pack of CC provided by the subject will be labeled to identify which subject the cigarettes belong to (labels should be affixed by the study site collaborator to the cellophane wrapper of the lower part of the pack). Each pack of CCs will be labeled to identify necessary information to match the subject with its suppliers.

For the Tobacco Sticks, the packs and cartons will be pre-labeled with the necessary information, including, product code. The labels will be translated into Japanese. See (Appendix 4).

Confidentiality statement: Data and information contained in this document are considered to constitute trade secrets and confidential commercial information, and the legal protections provided to such trade secrets and confidential information are hereby claimed under the provisions of applicable law. No part of this document may be publicly disclosed without the written consent of Philip Morris Products S.A.

6.2 Use of Investigational Product

Subjects will never be requested or forced to smoke and will be free to stop smoking at any time during the study. The study is designed as an *ad libitum* use study. During the confinement period, smoking will generally be allowed between 06:30 AM to 11:00 PM. During the screening period, subjects will be allowed to smoke according to their smoking habits except during the procedures of the screening Visit at the discretion of the site.

6.2.1 Run-in Period

Smoking *ad libitum* will be allowed prior to admission and throughout the day except during the procedures. All subjects will be allowed to continue smoking *ad libitum* their single preferred brand of usual CC. All subjects (except women with a positive pregnancy test at Screening or at Admission) will undergo a THS 2.2 product test prior to enrolment.

Following the confirmation that the subject is able and willing to use the THS 2.2 product, subjects will be enrolled.

6.2.2 Baseline Period

During the baseline period, all subjects will be allowed to continue smoking *ad libitum* their single preferred usual brand of non-menthol CC.

6.2.3 Exposure Period

Subjects are not allowed to smoke any CC or use any nicotine/tobacco-containing products other than the product/regimen.

6.2.3.1 THS 2.2 Arm

Subjects randomized to the THS 2.2 arm will use exclusively THS 2.2 from Day 1, 06:30 AM onwards until Day 5, 11:00 PM.

6.2.3.2 Conventional Cigarettes Arm

Subjects randomized to the CC arm will continue smoking their CC from Day 1, 06:30 AM onwards until Day 5, 11:00 PM.

6.2.3.3 Smoking Abstinence Arm

Subjects randomized to the SA study arm will be instructed to abstain from smoking from Day 1, 06:30 AM onwards until Day 5, 11:00 PM. They will not be provided with medication supportive for smoking abstinence.

6.2.4 Stopping Rules for Investigational Product

For safety purposes, smoking should be temporarily stopped in the event of any signs suggesting nicotine overexposure, (e.g., gastrointestinal disturbance [nausea, vomiting, diarrhea, stomach or abdominal pain], cold sweats, headache, dizziness, and breathing problems) or any reasons at the discretion of the Investigator.

6.2.5 Safety Follow-up Period

During the safety follow-up period (after the Time of Discharge at Day 6 until Day 13), all subjects are free to smoke their own CC *ad libitum*. Subjects in the SA arm, who wish to continue their SA, or any subject who wish to stop smoking will be referred for further treatment as per the standard of care in the country in which the study is conducted, if requested by the subject.

6.3 Method for Assigning Subjects to Study Arms

When all the eligibility criteria have been met, randomization will be done through the Interactive Web and Voice Response System (IWRS) on Day 0 at any time during the day. Subjects will be informed of their randomized study arm in the morning of Day 1, prior to 06:30 AM.

Subjects will be randomized in one of the three study arms THS 2.2:CC:SA in a 2:1:1 ratio. Stratified randomization will be conducted by sex and by average daily cigarette

Confidentiality statement: Data and information contained in this document are considered to constitute trade secrets and confidential commercial information, and the legal protections provided to such trade secrets and confidential information are hereby claimed under the provisions of applicable law. No part of this document may be publicly disclosed without the written consent of Philip Morris Products S.A.

consumption in the 4 weeks prior to the Screening Visit (those smoking 10 to 19 CC and those smoking >19 CC per day) reported by the subject. In each arm, each sex and each of the smoking strata should have a quota applied to ensure they represent at least 40% of the population.

6.4 Blinding

This is an open-label study; therefore, the subjects and Investigators will be unblinded to the subject's arm. However, there will be a limited degree of blinding in the data review and data analysis process. In particular, PMI and CRO personnel will be blinded to the randomized arm as summarized in the following table:

Blinded Study Personnel	End of Blinding Period
PMI and CRO study statisticians	After the statistical analysis plan (SAP) finalization or PMI blind database review ^(*) , whichever comes last.
PMI data manager	After the finalization of PMI blind database review. ^(*)
PMI safety and clinical scientists	After the finalization of PMI blind database review ^(*) . Can be actively un-blinded before that time point in case of the occurrence of any safety question, when appropriate.

(*) As part of the PMI quality control (QC) activity, data listings will be reviewed by PMI before database lock, with no access to the randomization arm information.

Any PMI and CRO personnel who are not listed in the above table will be unblinded by default.

6.5 Investigational Product Accountability and Compliance

6.5.1 Dispensing Investigational Product

From Day-2 onwards, each CC will be dispensed to the subjects. Subjects in the THS 2.2 arm will be provided by the site personnel with Tobacco Sticks from Day 1 to Day 5. One cigarette/tobacco stick will be allowed at a time, as per the study design, and documented in an appropriate Log.

On each day of the confinement period, the time of dispense and the time of return for each product has to be documented from Day-1 for CC and from Day 1 for Tobacco Sticks

Confidentiality statement: Data and information contained in this document are considered to constitute trade secrets and confidential commercial information, and the legal protections provided to such trade secrets and confidential information are hereby claimed under the provisions of applicable law. No part of this document may be publicly disclosed without the written consent of Philip Morris Products S.A.

onwards. The start of product use will correspond to the time of dispense of the first CC/Tobacco Stick. The subject must not take a puff of the tobacco stick during the pre-heating time. The product will not be promoted for commercial distribution or test market.

6.5.2 Storage and Accountability

The study collaborator (the investigational product storage manager) designated by the head of the investigational site will be responsible for the storage and accountability of the investigational products.

The THS 2.2 and CC will be stored in a secured storage site with access limited to authorized personnel only. Full accountability of the distributed products will be ensured by designated IP storage manager. Subjects will return each butt of CC and any used Tobacco Stick immediately after use. This will be documented in appropriate log.

All tobacco plugs of all used Tobacco Sticks will be separated from the filters and the tobacco plugs will be collected from Day 1 to Day 5, using dedicated vials for accountability and subsequent analysis of potential combustion occurrences 7.8.2.

6.5.3 Investigational Product Retention

The study site will destroy or return to the Sponsor any unused Tobacco Sticks and will return to the Sponsor the THS 2.2 product components upon study completion. Retention of THS 2.2 products will be documented.

Irrespective of the study arm on the time of Discharge from the clinic, the site study collaborator will return to the subjects any remaining CCs given by them on the Day of Admission.

6.5.4 Compliance to Investigational Product(s)

Compliance for all study arms will be ensured by strict distribution of the products (product by product) and collection of used Tobacco Sticks, the CC butts will be documented in appropriate log.

Confidentiality statement: Data and information contained in this document are considered to constitute trade secrets and confidential commercial information, and the legal protections provided to such trade secrets and confidential information are hereby claimed under the provisions of applicable law. No part of this document may be publicly disclosed without the written consent of Philip Morris Products S.A.

In addition, in the SA arm, compliance will be chemically verified using an exhaled CO breath test. The cut-off point for the CO breath test value to distinguish tobacco use vs no tobacco use will be 10 ppm (Benowitz et al., 2002).

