7.5.1.2 Plasma Nicotine and Cotinine

Nicotine and cotinine concentrations will be measured in plasma to evaluate the exposure to nicotine. For subjects in the SA arm, blood samples will be collected on Days 0 to 4, at comparable time points. No nicotine PK profile will be done for subjects in the SA arm on Day 5 and Day 6.

- On Day 0 to Day 4 (all study arms):

One blood sample for nicotine and cotinine will be drawn each day between 08:00 PM-09:30 PM.

- Nicotine/cotinine PK Profile on Day 5 and Day 6 (THS 2.2 and CC arms only):

In total, 9 blood samples will be drawn on Day 5. The first blood sample on Day 5 will be drawn within 15 minutes prior to the first product use (=T0). On Day 5, T0 will serve as a

Confidentiality statement: Data and information contained in this document are considered to constitute trade secrets and confidential commercial information, and the legal protections provided to such trade secrets and confidential information are hereby claimed under the provisions of applicable law. No part of this document may be publicly disclosed without the written consent of Philip Morris Products S.A.

reference for the time to peak concentration. An additional 8 blood samples will be drawn in 2-hour intervals after T₀. The last blood sample should be drawn no later than 11:00 PM, corresponding to the end of the product use period. At all time-points, if the subject wants to smoke around the time of the blood draw, he/she should smoke first and the blood will be drawn after the product has been used. Depending on the time of the first product use, it may be that fewer than 8 blood samples will be collected from a subject after T₀.

On Day 6, two blood samples will be drawn. The first one will be 20 hours after T₀ and the second blood sample will be 24 hours after T₀ (with T₀ being the time of the first product use on Day 5).

- On Day 5 and Day 6 (SA arm only):

On Day 5, one blood sample will be drawn between 08:00 PM-09:30 PM.

On Day 6, one blood sample will be drawn between 08:00 AM-09:30 AM.

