Subjects in the SA arm will be asked to abstain from using any nicotine/tobacco containing product and will not be provided with medication to support SA. Subjects will be provided with psychological support during the period of smoking abstinence.

The end of the 24-hour urine collection period for Day 5 will end in the morning on Day 6 prior to Discharge.

Subjects will be discharged from the investigational site in the morning of Day 6 after all safety examinations of the Day of Discharge have been conducted. Use of CC will be allowed on Day 6, but only after spirometry has been performed.

After Discharge, subjects will enter into a 7-day safety follow-up to capture spontaneously reported new AEs/SAEs and for active follow-up of ongoing AEs/SAEs. Any AE will in general be followed up until resolved, stabilized (i.e., no worsening of the event), or until a plausible explanation for the event has been found. The end of study (EOS) is defined as the end of the 7-day safety follow-up period.

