6.3.3 Compliance to Product Allocation

Compliance for all arms will be ensured by strict distribution of the products (product by product) and collection of used THS Tobacco Sticks and the CC butts after use will be documented in appropriate logs.

In addition, in subjects in the SA arm, the compliance will be chemically verified using exhaled CO breath. The cut-off point for the CO breath test value to distinguish subjects in the SA arm with CC use vs. no CC use will be 10 ppm (Benowitz et al. 2002). No subjects from the SA arm will be withdrawn from the study if their exhaled CO breath test results are >10 ppm.

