11.1 Major Protocol Deviations

Subjects with major protocol deviations will be identified (at a population level) to determine whether they will be excluded from any of the analysis populations. This will take place during the pre-analysis data review meeting prior to database lock. The following have been identified as the major protocol deviations.

The categories for the major deviations will include, but are not limited to the deviations presented in Table 14.

Table 14: Definition of Major Protocol Deviations

Category	Description
Mis-randomization	Being administered the wrong product according to the randomization schedule. Use of any nicotine or tobacco-containing product other than the assigned product.
Product compliance Violation	Exhaled CO breath test >10 ppm for subjects from the SA arm after Day 2
Duration of 24 hour collection	Violation of inclusion/exclusion criteria. Start and end times not within the 30 min window.

Among the above criteria, violations of inclusion criteria 5 to 7, or of the exclusion criteria 1, 3 to 16, and 18 will be assessed for their impact on the PP Population and evaluated during the pre-analysis data review meeting (Section 6.3.1 “Methods of Assigning Subjects to Product Arms”).

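### Apart from controlled dispensing, SA abstinence is checked only by breath CO at 10 ppm, which cannot detect unburnt, unheated nicotine and could miss THS 2.2 use, while the cotinine and NEQ already assayed have no compliance role

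*Protocol*

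**What the plan says.** Protocol 6.6.1 bars the SA arm from cigarettes and from every other nicotine or tobacco product, NRT included, from Day 1 to Day 5. SAP 6.1 agrees: "Subjects in the SA arm will be asked to abstain from using any nicotine/tobacco containing product".

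Protocol 6.5.4 sets two layers of control. The first is physical: "Compliance for all study arms will be ensured by strict distribution of the products (product by product) and collection of used Tobacco Sticks". The second is chemical: "In addition, in the SA arm, compliance will be chemically verified using an exhaled CO breath test". It then says what the test is for: "The cut-off point for the CO breath test value to distinguish tobacco use vs no tobacco use will be 10 ppm". SAP 6.3.3 instead says that the value to "distinguish subjects in the SA arm with CC use vs. no CC use will be 10 ppm", and SAP 12.4 gives the purpose as showing that no cigarettes were smoked. SAP 9 does not list this narrowing as a change from the protocol.

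A high reading has limited consequences. SAP 6.3.3 states: "No subjects from the SA arm will be withdrawn from the study if their exhaled CO breath test results are >10 ppm". SAP Table 14 counts as a major deviation: "Exhaled CO breath test >10 ppm for subjects from the SA arm after Day 2". Table 14 separately makes use of any non-assigned nicotine or tobacco product a major deviation, with no biochemical criterion attached. The planned compliance output, Table 15.2.5.1, shows exhaled CO alone.

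Other markers of nicotine intake are measured in the same subjects. Under Protocol 7.5.1.2, SA plasma nicotine and cotinine are sampled on the evenings of Days 0 to 4. The section continues: "On Day 5, one blood sample will be drawn between 08:00 PM-09:30 PM". A last sample follows on the morning of Day 6. Table A2 schedules NEQ in every daily 24-hour urine from Day -1 to Day 5. None of these appears in SAP 6.3.3, 10.2, 11.1 or 12.4.

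**The concern.** The regimen prohibits nicotine in any form, but the chemical check responds only to CO. A product that is neither burnt nor heated adds no CO, so no cut-off could detect it. THS 2.2 delivers some CO (0.6 to 1 mg per stick, Protocol Table 1), and the plan expects its users to have much lower COHb than smokers, so they may fall under a threshold that the SAP itself describes as one for cigarettes.

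The SA arm is the benchmark for how close THS 2.2 comes to abstinence (Protocol 2.1.1 and 2.2). Undetected THS 2.2 use in that arm would pull the THS 2.2/SA biomarker ratios towards 1. Undetected nicotine use of any kind would raise NEQ and could blunt withdrawal (MNWS) and urges (QSU-brief). Where the plan expects THS 2.2 to lie above abstinence, this makes THS 2.2 look closer to it.

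**Working it through.** **Inputs.** COHb mean ratios and CVs from Protocol 12.2 (Tables 16 and 17) and SAP 8: THS 2.2/CC 0.40 (0.32) and 0.44 (0.14); THS 2.2/SA 2.10 (0.20). They come from studies of earlier products and are assumed to carry over to THS 2.2. Arms: 80 THS 2.2, 40 CC, 40 SA.

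**1. Check the inputs against the plan's power figure.** The plan gives no figure for the sensitivity of the CO test, so I reproduced the power in Table 18, which rests on the same COHb ratios. With σ = √ln(1+CV²), SE = σ√(1/40+1/80), power = Φ(ln(0.50/MR)/SE − 1.96):

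- MR 0.40, CV 0.32: σ = 0.312, SE = 0.0605, ln(0.50/0.40) = 0.223, power 95.8% for COHb. The product over all four biomarkers is also 95.8%; the plan states 96%.
- MR 0.44, CV 0.14: σ = 0.139, SE = 0.0270, ln(0.50/0.44) = 0.128, power 99.7%; the plan states >99%.

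**2. Break-even against 10 ppm.** Assume that exhaled CO follows the COHb ratios. The average full-time THS 2.2 user stays at or below 10 ppm if:

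- the CC mean is at most 10/0.40 = 25.0 ppm, or 10/0.44 = 22.7 ppm;
- equivalently for the first ratio, the abstinent mean is at most 10/2.10 = 4.76 ppm.

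**3. Allow for spread.** Share of THS 2.2 users passing on one reading = Φ(ln(10/(MR × CC mean))/σ). The CC means are assumptions, because the documents give no ppm level for any arm.

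| Assumed CC mean (ppm) | THS 2.2 mean, MR 0.40 / 0.44 (ppm) | Share passing, MR 0.40 CV 0.32 / MR 0.44 CV 0.14 |
|---|---|---|
| 15 | 6.0 / 6.6 | 95% / >99% |
| 20 | 8.0 / 8.8 | 76% / 82% |
| 25 | 10.0 / 11.0 | 50% / 25% |
| 30 | 12.0 / 13.2 | 28% / 2% |
| 40 | 16.0 / 17.6 | 7% / <1% |

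These rows describe full ad libitum use. A lapse of a few sticks would add less CO and be harder to detect.

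**4. Effect on the THS 2.2/SA ratio.** If a fraction f of SA subjects sits undetected at the THS 2.2 level, the geometric mean ratio R becomes R^(1−f).

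| Biomarker (assumed ratio) | f = 1/40 | f = 10% |
|---|---|---|
| COHb (2.10) | 2.06 | 1.95 |
| 3-HPMA (1.70) | 1.68 | 1.61 |
| S-PMA (1.15) | 1.15 | 1.13 |
| MHBMA (1.00) | 1.00 | 1.00 |

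For scale, the expected 95% CI half-width for the COHb THS 2.2/SA ratio is exp(1.96 × 0.198 × √(1/40+1/80)) − 1 = 7.8%. One full-time user in 40 shifts the ratio by about 2% (2.06/2.10 = 0.98). Four in 40 shift it by about 7% (1.95/2.10 = 0.93), roughly the half-width.

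**5. Where the flag acts.** Table 14 feeds only the PP population. PP is used only for robustness of the primary endpoint, and only if more than 10 subjects are excluded (SAP 10). The THS 2.2 vs SA analyses of BoExp, NEQ, QSU-brief and MNWS are on the FAS, where membership does not depend on compliance (SAP 10.1). A new flag alone would therefore change none of them.

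**The case against.** The strongest reply is that CO is a supplement. Subjects are confined. They hand over their cigarettes in sealed packs at admission. Products are kept in secured storage, dispensed singly with times logged, and returned immediately after use. SA subjects have no access to the smoking rooms (Protocol 6.1.3, 6.5.1, 6.5.2, 6.6.1). Sustained THS 2.2 use in the SA arm would need unlogged sticks and a Holder. Use of another product is already a major deviation whatever the CO value, the Table 14 list is not exhaustive, and SAP 11 allows further deviations to be found in the data. Plasma nicotine and cotinine are listed, NEQ is tabulated, and the title of Table 15.2.5.1 names exhaled CO. All of this stands, so it would be wrong to say that CO is the only check. But dispensing logs cover only what the site holds, and the protocol chose to add chemical verification of tobacco use. No criterion says what cotinine or NEQ pattern would count as a lapse.

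A reader might infer from the 2.10 ratio that a full-time THS 2.2 user would pass, or that the test has almost no sensitivity. The documents do not support either. A ratio cannot be set against an absolute cut-off without a ppm level. Even at an abstinent mean of 4 ppm (THS 2.2 mean 8.4), CVs of 0.20 to 0.32 put 19% to 29% of users above 10 ppm on a single reading, and four readings are taken each day. Very low abstinent levels are also hard to credit: below 10 × 0.40/2.10 = 1.9 ppm, continuing smokers themselves would average under 10 ppm. A similar claim about one cigarette needs a CO half-life that the documents do not give.

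**Conclusion.** The point holds in limited form. Exhaled CO is the only prespecified biochemical check on SA abstinence. The two documents disagree on what it tests, and it cannot cover the full prohibition. That it misses unburnt, unheated nicotine needs no ppm assumption. That it misses THS 2.2 is a possibility, conditional on a CC mean below about 23-25 ppm (abstinent mean below about 4.8 ppm), on exhaled CO scaling like COHb, and on the earlier-product ratios applying to THS 2.2.

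The consequence is confined to the secondary and exploratory THS 2.2 vs SA comparisons. It is small for biomarkers unless several subjects lapse. The effect of NRT-type use on NEQ, MNWS and QSU-brief cannot be sized from the documents. A reader might infer a threat to the success criterion. There is essentially none, because that criterion compares THS 2.2 with CC and SA data enter the primary model only through its common terms (SAP 12.6). The change is worth making because the data already exist.

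**What to change.** 1. Reconcile Protocol 6.5.4 with SAP 6.3.3 and 12.4, so that the CO test is described as a test for CC smoking.
2. Keep the CO rule. Add to SAP Table 14 and Table 15.2.5.1 a prespecified SA flag for a rise, or no fall, in plasma cotinine between consecutive samples from Day 2 evening to Day 6 morning (five samples, four comparisons), shown beside NEQ. State the assay-error margin. It matters most for the last pair, which is only 10.5 to 13.5 hours apart by the sampling windows. Exempt consecutive values below LLOQ: SAP 7.1 sets both to LLOQ/2, so they would be equal and flag a subject who may be fully abstinent. The rule assumes that cotinine falls steadily by then without intake, which the bioanalytical team should confirm.
3. Repeat the THS 2.2 vs SA analyses (BoExp, NEQ, QSU-brief, MNWS) as a sensitivity analysis without flagged SA subjects. Without this step the flag reaches none of those results.

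Cost: wording, one derived flag and one more set of tables. A few SA subjects may be flagged. No new samples or assays are needed.
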